acid (UDCA) could enhance the bile synthesis by CYP7A1 altering the gut microbiota population. UDCA also has other beneficial effects, such as anticholestatic, antifibrotic, antiproliferative, and anti-inflammatory [12-14].

In retrospective studies, statins appear to be safe in patients with compensated cirrhosis, and evidence suggests that they may significantly reduce fibrosis (HR:0.56, p<0.0001)[15]. Preclinical data from studies performed on in vitro and in vivo animal models shed light on favorable effects of statins on endothelial function, angiogenesis, PHTN, and fibrosis. Suggested mechanisms involve regulation of KLF2, eNOS, thrombomodulin, and C-natriuretic peptide. Animal studies evidence suggests that the administration of fluvastatin, lovastatin, and simvastatin to primary rat hepatocytes and human hepatoma cell line inhibits the paracrine activation of HSCs [16], reduces HSC turnover and activity [17,18]. Moreover, Nature (2020) reported statin therapy is associated with lower prevalence of gut microbiota dysbiosis. [19]

The combination of ursodeoxycholic acid and statins is safe in human experiments, and the combination of the two has also proved to have a synergistic effect on the reduction of bile cholesterol levels [20], but there is no research on improving fibrosis makers or improving intestinal flora.

The goal of the current study was to evaluate our hypothesis model of pathogenesis of chronic inflammation of liver cirrhosis. We hypothesized that an adverse microbiome would exacerbate the histopathological severity of liver induced by CCL4 in a germ-free mice model. We transplanted these mice with human fecal samples from healthy controls, or liver cirrhosis treated with statin, or UDCA. The clinical trial mainly explores whether single statin or combined ursodeoxycholic acid can reduce liver fibrosis indicators, inflammatory cytokines and intestinal flora imbalance in patients with liver cirrhosis who have been cured of chronic hepatitis C or non-viral load hepatitis B.

Patients and assessments- Study design

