We expect to enroll 120 stable patients who have achieved sustained viral response (SVR) (ie, viral eradication) after hepatitis C treatment for 6 months, or non-viral load hepatitis B for 6 months, who have been diagnosed with primary cirrhosis (FIB-4 \geq 3.25) and met the Baveno VII criteria (liver stiffness measurement [LSM] \geq 25 kPa) and exclude it (LSM <15 kPa and platelet count [PLT] \geq 150 \times 10⁹/L) were used. Grey zones were classified into two groups: (high – LSM between 20–25 kPa and PLT <150 \times 10⁹/L, or LSM between 15–20 kPa and PLT <110 \times 10⁹/L, or low – defined as the remaining patients within the grey zone) [27]. **Exclusion conditions:** already taking statins, diabetes, liver cancer, alcoholic liver, moderate to severe fatty liver, liver decompensation (jaundice, ascites, esophagogastric varices, history of hepatic coma), chronic kidney disease, antibiotic use within three months and gastric ulcer medication(such as PPIs). Randomly divided into three groups: **Group 1:** control group (n =

30), Group 2: treatment group (ursodeoxy Cholic acid (UDCA) (10mg/kg/day) (n = 30), Group 3: treatment group (simvastatin 40mg) (n = 30), Group 4: treatment group (simvastatin 40mg/day + ursodeoxy Cholic acid (UDCA) (10mg/kg/day) (n = 30). Fecal bile acid content and fecal flora, skin bile acid profile, cytokine markers, biochemical fibrosis biomarker were collected at the test base point and six months after treatment. In addition, patients who achieved virus eradication without liver cirrhosis (FIB-4 < 1.45, n=30) collected the content of fecal bile acid, fecal flora, skin bile acid, and inflammatory cytokines were collected at the test base point index, biochemical fibrosis biomarkers. Analysis of flora: 16S ribosomal RNA gene sequence analysis from the patient's fecal tube. Analysis of total fecal bile acid: LC-MS/MS system analysis. Skin bile acid profile:Desorption-Electrospray Ionization Mass Spectrometry (TD-ESI/MS).

Block randomization

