Patients (n=120) were distributed on one block with 8 numbers and each group contained two numbers (1, 2, 3, 4). The admitted patients who were eligible for inclusion were given numbers in the order; number 1 was allocated to (control group) as the study group, patients who carried number 2 was allocated to (UDCA group),patients who carried number 3 was allocated to (simvastatin group), and number 4 was allocated to (simvastatin plus UDCA group). Therefore, the control and three interventional groups were randomized into 1:1:1:1.

Stool sample preparation and microbiota analysis

Bile juice and biliary stents samples will be collected in separate sterile containers containing 2mL of RNA later and will be stored at room temperature. The samples will be transferred to the laboratory within 12 h, stored at 4°C, and used for extracting DNA within few weeks. Preliminary experiments will confirm that the bacterial composition data does not change in four weeks under the storage conditions used. Genomic DNA will be isolated from stool samples using the CTAB/SDS methods (Novogene Laboratories) following the manufacturer's protocol. All microbial community DNA samples will be analyzed for V4 variable region of bacterial 16S ribosomal RNA gene using PCR primers 515F and 806R. The PCR products will be separated by 2% agarose gel electrophoresis. Samples with bright main strip between 400-450bp will be chosen for further experiments. PCR product will be mixed in equidensity ratios. Then, mixture PCR products will be purified with Qiagen Gel Extraction Kit (Qiagen, Germany). Sequencing libraries will be generated using TruSeq DNA PCR-Free sample Preparation Kit (Illumina, USA) following manufacturer's recommendations and index codes will be added. The library quality will be assessed on the Qubit® 2.0 Fluorometer (Thermo Scientific) and Agilent Bioanalyzer 2100 system. At last, the library will be sequenced on an IlluminaHiSeq2500 platform and 250 bp paired-end reads will be generated.

Fecal bile acid profile [20].

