TD-ESI source comprised of a direct probe (DP), thermal desorption unit, and electrospray ionization device. First, the direct probe (DP) was used for sampling analytes in solution or on solid surfaces. For liquid samples, a stainless steel inoculating loop serving as a probe (2 mm in diameter) was used to obtain approximately 2 μ L of sample solution for each analysis. For viscous solutions or solid samples, a straight fine needle (350 μ m in diameter) was used to either collect analytes of viscous solutions or sweep five times across solid surfaces to obtain analytes. Second, the function of the thermal desorption unit was to vaporize samples on the DP and introduce desorbed analytes into the ESI plume through a quartz tube with single taper (OD= 6 mm, ID= 4 mm, Length= 80 mm) so that effective sample ionization can take place. In addition, an opening in the thermal desorption unit was created when the direct probe was removed from the unit to sample analytes. The thermal desorption unit was sealed after the direct probe was placed back on the thermal desorption unit for analysis of sample analytes on the probe. Third, an electrospray ionization device was used for post-ionizing desorbed analytes. The high voltage and solvent flow rate required to generate an electrospray plume were 5 kV and 2.5 μ L/min, respectively. The ESI solution was a methanol and water mixture (1:1, v/v) containing 0.1% acetic acid, and was delivered through a fused-silica spray capillary (ID= 100 μ m, OD= 375 μ m, Polymicro, Phoenix, AZ) into the mass inlet of the mass spectrometer. The TD-ESI source was attached to a triple quadruple mass spectrometer (Agilent 6410) to detect the analyte ions. To obtain a stable solvent and analyte ion signal, the electrospray capillary was aligned to the MS inlet and the distance from the exit of the TD tube to the electrospray capillary (d_1) was kept at 8 mm, while the distance from the MS inlet to the electrospray capillary (d_2) was 5 mm. The temperature in the thermal desorption unit was set at 250 °C and was measured by a thermistor installed in the source. The flow rate of the nitrogen gas used to deliver desorbed analytes into the ESI plume was 0.8 L/min.

Primary end point: Fibrosis biomarker [23]

Molecular markers of fibrogenesis including TGF- β 1, and Type IV collagen. Hyaluronic Acid in the serum blood test, and clinical laboratory FIB-4 Index.

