Secondary end points: 1. Cirrhosis dysbiosis ratio (CDR), the ratio of autochthonous good bacteria (e.g. Lachnospiraceae, Ruminococcaceae and Clostridiales) to non-autochthonous/ pathogenic bacteria (e.g. Enterobacteriaceae and Streptococcaceae). 2. Total stool bile acid, Secondary and primary bile acid ratio. 3. Serum inflammation peptides (IL-6, IL-8, IL-10, and TNF-a)

Sample size : Till now, there was no prospective data to support the evaluation the sample size of study in the liver fibrosis deminition after the administrations of stain and UDCA. Prior data [24]may indicate the effect of 40 mg simvastatin versus placebo on hepatic portal pressure was studied over a period of 3 months. A significant decrease in HVPG (-15%) was noted in the experimental group versus no change in the placebo group. The study included 24 cases in each study arm. Therefore, we plan to enroll 30 participants in each arm.

Safety

Initial dose of study drug is 20 mg which can be increased to 40 mg after 4 weeks if the participant does not develop side effects. Creatine kinase and standard biochemistry including liver enzymes are measured for safety reasons after 2 weeks, to rule out myositis and liver damage. Side effects and events are consecutively registered throughout the trial. Safety of statins in chronic liver disease has been assessed in only a few clinical trials, but reviews of observational studies report high safety and low risk of adverse events, even significantly lower the all-cause mortality [25,26]

Statistical analysis:

Risks are reported as IRRs along with their 95% confidence intervals and P values. For subgroup analyses according to sample characteristics, P values for interaction also are assessed. The cumulative proportion of patients developing liver fibrosis events during follow-up is estimated by life table methods and log-rank tests were reported. P values are 2-sided, and values of .05 or less are considered statistically significant. All statistical analyses are performed using SAS version 9.1 (SAS Institute Inc).

Limitation 1:

If post treated human feces contain the trace level of drug, the hypothesis that it is caused by microorganisms alone does not hold. We will check the post treated human feces by the TD-ESI (LTQ)for simvastatin (Formula: $C_{25}H_{38}O_5$, Exact mass: 418.57 Da),and Ursodeoxycholic acid (UDCA)(Formula : $C_{24}H_{40}O_4$. Exact mass : 392.29 Da). The pre-test was performed by TD-ESI (LTQ) as followed figures.

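### The primary end point is four fibrosis markers with no lead marker or combining rule, and the stated analysis is for undefined events, so the primary result has no matching test and no defined false positive rate

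*Protocol*

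**What the plan says.** **End point.** Under its heading for the primary end point, a fibrosis biomarker, the Protocol lists "Molecular markers of fibrogenesis including TGF- β 1, and Type IV collagen", followed by "Hyaluronic Acid in the serum blood test, and clinical laboratory FIB-4 Index". That makes four laboratory variables under one label. No marker leads, no composite is defined, and nothing says whether one or all must improve. The word introducing the first two also leaves the list open.

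**Timing.** The Study design section says that "biochemical fibrosis biomarker were collected at the test base point and six months after treatment".

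**Arms.** Under Block randomization, "the control and three interventional groups were randomized into 1:1:1:1", with 30 patients in each. No primary contrast is named. The last paragraph of the introduction gives the aim: "The clinical trial mainly explores whether single statin or combined ursodeoxycholic acid can reduce liver fibrosis indicators". That can be read as naming two regimens, simvastatin alone and the combination.

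**Analysis.** The Statistical analysis section promises IRRs with confidence intervals and P values, interaction tests for subgroups, and this: "The cumulative proportion of patients developing liver fibrosis events during follow-up is estimated by life table methods", with log-rank tests. It closes its account of inference with "P values are 2-sided, and values of .05 or less are considered statistically significant". It gives no definition of a fibrosis event and no method for comparing marker levels between arms.

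**The concern.** There are two linked faults.

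First, the stated methods do not address the primary end point. A life table and a log-rank test need an event and a time to it. The markers are continuous values measured at two planned visits. No cut-off turns any of them into an event, and the patients are enrolled with cirrhosis already diagnosed, so what it would mean to develop a fibrosis event is not clear either.

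Second, whatever test is eventually used, the Protocol does not say which marker, or how many, in which arm, would make the primary result positive. With four markers and three active arms there are 12 comparisons with control to choose from, and the only decision rule given is the .05 threshold.

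At stake is the reading of a positive marker. A report that one marker fell significantly in one arm would be taken as a 5% claim, and the Protocol gives no basis for that or any other error rate.

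**Working it through.** **The plan's own figure.** The only design figure is 30 per arm. It cannot be reproduced for the markers: the Sample size section cites a portal-pressure study with 24 per arm and a 15% fall, and gives no SD, power, dropout rate or effect on any of the four markers. The only error figure is the .05 two-sided threshold.

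**Do the stated methods fit?** Side by side:

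| Primary end point needs | Statistical analysis gives |
|---|---|
| A between-arm comparison of a continuous value at six months | IRRs for risks |
| Use of the baseline value already collected | Life tables and log-rank tests for events |
| One variable, or a rule for combining four | A threshold for P values |

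No entry on the right tests anything on the left.

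**Range of false positive rates.** Inputs from the Protocol: 4 markers, 3 active arms, 1 control, 30 per arm, two-sided 0.05. Assumptions, because the Protocol gives none: t-tests, normal markers, equal correlation between markers, no treatment effect anywhere.

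With independent tests the chance of at least one P ≤ 0.05 is 1 − 0.95^m:
- m = 1: 5.0%
- m = 4 (one contrast): 1 − 0.95^4 = 18.5%
- m = 12 (three contrasts): 1 − 0.95^12 = 46.0%

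The tests share a control arm and the markers may be correlated, so simulation (200,000 null trials) is more realistic:

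| Success rule | Correlation 0 | 0.5 | 0.9 |
|---|---|---|---|
| Any marker, any of 3 arms, either direction | 41.5% | 35.6% | 22.5% |
| Same, benefit only | 22.9% | 18.2% | 11.3% |
| Any marker, simvastatin or combination, either direction | 31.6% | 26.8% | 16.7% |
| Same, benefit only | 16.9% | 13.6% | 8.4% |
| All four markers better in at least one of 3 arms | 0.0% | 0.2% | 2.5% |
| All four better in simvastatin or combination | 0.0% | 0.1% | 1.8% |

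The all-four rule has no ceiling at 2.5%. For three arms it rises to about 3.5% at correlation 0.95, 4.9% at 0.99 and 6–7% at 1.0. At 1.0 the four markers act as one. One marker tested unadjusted in three arms gives 12.5% in either direction, so about 12.5/2 = 6.2% for benefit, which agrees.

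**Power cost of adjusting across arms.** With 30 per arm and 80% power (noncentral t, 58 df), the detectable difference is:
- one primary contrast, alpha 0.05: 0.74 SD
- first Holm step over two contrasts, alpha 0.05/2 = 0.025: 0.81 SD
- first Holm step over three contrasts, alpha 0.05/3 = 0.0167: 0.86 SD

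Baseline adjustment multiplies each by √(1 − r²). At an assumed baseline to six-month correlation r = 0.5 the factor is √0.75 = 0.866: 0.736 × 0.866 = 0.64 SD for one contrast and 0.857 × 0.866 = 0.74 SD for three. At the difference that one unadjusted contrast detects with 80% power, the first Holm step over three has about 65%; about 41 per arm would restore 80%.

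**The case against.** The strongest reply is that testing order, multiplicity and the model are commonly left to a SAP, which is not shown, and that the .05 sentence is a convention that does not rule out adjustment, since adjusted P values are also compared with .05. This stands in part. The absence of a multiplicity procedure is not by itself a fault, and reading the sentence as applying unadjusted to every marker in every arm is an inference. What remains is in the Protocol's own text: it defines a four-part primary end point without a rule, and it states methods that do not analyse that end point. A SAP would have to override that text.

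A reader might infer from the table that the trial's false positive rate is inflated to 23%, or 41% counting both directions. The document does not support that. It nowhere says that any marker in any arm counts as success, and the all-four reading gives rates below 5% over most of the assumed correlations. A reader might also conclude that correction across the three arms is obligatory. Whether distinct treatments against a shared control need it is debated, and the stated aim can be read as naming only two regimens.

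Finally, the aim is worded as exploration and no power is claimed. That limits the consequence, but the Protocol still declares a primary end point and a significance threshold, so readers will expect the two to be connected.

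**Conclusion.** The point holds as a mismatch and an undefined rule. As written, the primary analysis does not test the primary end point, and the false positive rate of the primary result is undefined. Depending on the success rule chosen later, the chance of a false benefit could lie anywhere from near 0% to about 23% for marker correlations between 0 and 0.9. That span rests on assumed t-tests, normality, equal correlations and no effect in any arm; it shows how much the missing rule matters and is not a property of the trial. This should be fixed because it limits how a positive marker can be interpreted. It does not invalidate the trial, the randomisation or the planned samples.

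**What to change.** **Primary end point section.** Name one of the four listed markers as the primary variable before six-month data are analysed. Make the other three secondary and close the list. A composite or an all-four rule would also define the error rate, but a composite needs weights the Protocol does not supply, and the all-four rule's error rate depends on unknown correlations.

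**Statistical analysis section.** For the markers, replace the IRR, life-table and log-rank text with ANCOVA of the six-month value on arm and baseline value, on a scale fixed in advance (log if skewed). Name the primary arm contrast or contrasts. Limit the .05 claim to those tests and give estimates with 95% confidence intervals for everything else. If more than one active-versus-control contrast is primary, state whether error is controlled across them; Holm is one option, not a requirement.

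**Cost.** No new samples, visits or patients, since both samples are already planned. One lead marker with one primary contrast carries no multiplicity cost. Holm raises the first-step detectable difference from about 0.74 SD to 0.81 SD (two contrasts) or 0.86 SD (three) before baseline adjustment; ANCOVA improves precision but does not remove that relative loss. No stated power is broken, because none is stated.

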There is emerging evidence that the gut milieu plays an important role in the progression of complications of cirrhosis [1–3]. Studies have found dysbiosis in the gut microbiota in patients with cirrhosis that has the potential to influence complications such as hepatic encephalopathy [1,2]. The gut milieu in cirrhosis involves the interaction between the microbiota and secreted factors, such as bile acids (BAs) that can also modulate the gut barrier [4]. The gut microbiota is known to convert 7a-dehydroxylate primary BAs and chenodeoxycholic acid (CDCA) and cholic acid (CA) into the secondary bile acids lithocholic acid (LCA) and deoxycholic acid (DCA), respectively [5]. Cirrhotic patients have been shown to have a lower proportion of secondary BAs in their bile but the mechanism for this is not clear [6]. Since BAs have important downstream pathophysiologic effects, a better understanding of the interaction between the intestinal microbiome and BAs is important to gain insight into the pathophysiology of cirrhosis [7,8]. In Genta Kakiyama study[9], the median abundances of taxa are shown with significantly higher Enterobacteriaceae and Veillonellaceae and lower autochthonous bacteria (Blautia, Ruminococcaceae, Lachnospiraceae) in cirrhotics, especially advanced cirrhotics compared to healthy controls. The total bile acid was 206.5 µg/100 mg dry stool in healthy control, and 39.0 in advanced cirrhosis. The secondary BAs were present in a significantly lower percentage of cirrhotics. The ratios of all secondary to primary BAs, and specifically of DCA/CA and LCA/CDCA, were also the lowest in advanced cirrhosis. Cirrhosis dysbiosis ratio (CDR), the ratio of autochthonous/good bacteria (e.g. Lachnospiraceae, Ruminococcaceae and Clostridiales) to non-autochthonous/ pathogenic bacteria (e.g. Enterobacteriaceae and Streptococcaceae), is significantly higher in controls and patients with compensated cirrhosis than patients with decompensated cirrhosis. Increasing CDR could lead to develop the hepatic encephalopathy[10]. Bile acids are also the endogenous ligands of Farnesoid X receptor (FXR), Takeda G protein receptor 5 (TGR5) and Sphingosine-1-phosphate receptor 2 (S1PR2). These receptors are placed at the interface of the host immune system with the intestinal microbiota and are highly represented in cells of innate immunity such as intestinal and liver macrophages, dendritic cells and natural killer T cells[11]. In human study, ursodeoxycholic

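### Limitation 1 labels simvastatin's average mass as its exact mass, and does not say how UDCA in stool is told apart from bile acids of identical mass

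*Protocol*

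**What the plan says.** Limitation 1 of the protocol sets a condition on the fecal-transplant argument: "If post treated human feces contain the trace level of drug, the hypothesis that it is caused by microorganisms alone does not hold". To meet it, the protocol says "We will check the post treated human feces by the TD-ESI (LTQ)for simvastatin" and for UDCA.

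Each drug is followed by a formula and a mass. Simvastatin is C25H38O5 with "Exact mass: 418.57 Da". UDCA is C24H40O4 with "Exact mass : 392.29 Da". The section adds "The pre-test was performed by TD-ESI (LTQ) as followed figures", but those figures are not in the text available. The visible text gives no ion, fragment, mass window, detection limit or decision rule for the check.

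Three other places bear on it:
- The introduction describes gut bacteria converting "primary BAs and chenodeoxycholic acid (CDCA) and cholic acid (CA") into the "secondary bile acids lithocholic acid (LCA) and deoxycholic acid (DCA), respectively".
- The section on the skin bile acid profile holds the only operating description of TD-ESI: a direct probe, thermal desorption, then electrospray into a triple quadrupole. It mentions no chromatography.
- The study design section plans a different method for stool bile acids, "Analysis of total fecal bile acid: LC-MS/MS system analysis", on samples taken at baseline and six months. The section on the fecal bile acid profile describes that method.

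**The concern.** The two masses carry the same label and stand in the same sentence, but they do not follow the same convention. Anyone who sets up or audits the assay from the printed simvastatin figure would be working 0.30 Da away from the true exact mass.

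The UDCA question is separate and more important. Stool contains bile acids whether or not a patient takes UDCA. If some of them have exactly UDCA's formula, a mass signal alone cannot say whether the drug is present. UDCA is given in two of the four arms, 30 + 30 = 60 of 120 patients, and stool from UDCA-treated patients is one of the materials to be transplanted into germ-free mice.

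What is at stake is the inference that any effect in the mice comes from the transplanted microorganisms and not from residual drug. The primary end point, sample size, randomization and error rate are not affected.

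**Working it through.** **Inputs.** The formulas and stated masses come from Limitation 1. The atomic masses are standard constants that the protocol does not print: monoisotopic C 12, H 1.007825, O 15.994915; average C 12.011, H 1.008, O 15.999.

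**Step 1: reproduce the stated simvastatin figure, C25H38O5.**
- Monoisotopic: 25 × 12 + 38 × 1.007825 + 5 × 15.994915 = 300 + 38.297 + 79.975 = 418.272 Da.
- Average: 25 × 12.011 + 38 × 1.008 + 5 × 15.999 = 300.275 + 38.304 + 79.995 = 418.574 Da.

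The stated 418.57 matches the average mass and not the exact mass.

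**Step 2: the same for UDCA, C24H40O4.**
- Monoisotopic: 24 × 12 + 40 × 1.007825 + 4 × 15.994915 = 288 + 40.313 + 63.980 = 392.293 Da.
- Average: 24 × 12.011 + 40 × 1.008 + 4 × 15.999 = 288.264 + 40.320 + 63.996 = 392.580 Da.

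The stated 392.29 is a true exact mass, so the sentence uses two conventions under one label.

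**Step 3: size of the simvastatin slip.** 418.57 − 418.272 = 0.298 Da, and 0.298 / 418.272 is about 713 parts per million. For the protonated ion, the exact mass gives m/z 419.279 and the average mass gives 419.58, again a shift of 0.30. The protocol states no window, so a range is needed:
- A window of ±0.5 Da centred on the printed figure still contains the ion.
- A window narrower than about ±0.30 Da centred on the printed figure misses it.

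**Step 4: which bile acids share UDCA's mass?** The isomer formulas are basic chemistry and are not printed in the protocol.

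| Bile acid named in the introduction | Formula | Exact mass (Da) | Difference from UDCA (Da) |
|---|---|---|---|
| CDCA | C24H40O4 | 392.293 | 0 |
| DCA | C24H40O4 | 392.293 | 0 |
| CA | C24H40O5 | 408.288 | 15.995 |
| LCA | C24H40O3 | 376.298 | −15.995 |

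Two of the four are indistinguishable from UDCA by mass, and better mass resolution would not help.

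**Step 5: would a before-and-after comparison at 392.29 Da be enough?** Not by mass alone. Total stool bile acid and the ratio of secondary to primary bile acids are secondary end points, so the trial itself looks for treatment-related change in endogenous bile acids. A rise at 392.29 Da could be carry-over of UDCA or a change in CDCA or DCA. Nor can untreated stool be assumed silent: the introduction cites total bile acid of 39.0 µg per 100 mg dry stool even in advanced cirrhosis. That figure is a total and not the amount of CDCA plus DCA.

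**The case against.** The strongest reply is that the masses merely describe the compounds. Both are neutral masses, while an electrospray instrument detects ions, so neither number can literally be the acquisition setting. The protocol does not say that detection is centred on them, and it reports a pre-test whose figures are missing from this text. Those figures may show the ions or fragments actually used. All of this stands. A reader might infer that simvastatin would be missed and contaminated stool wrongly cleared. The document does not support that, because it would require both that the acquisition was derived from the printed figure and that the window was narrower than about ±0.30 Da.

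It is also fair to say that the TD-ESI description belongs to the skin method on a triple quadrupole, while the stool check names an LTQ. The text does not say that the stool check rests on intact mass alone, and it states no presence-or-absence rule. A reader might go on to conclude that the whole check is incapable of working, or that it fails for both drugs. Neither is shown.

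What the reply does not remove is the isomer problem. The visible text assigns UDCA detection in stool to TD-ESI, identifies UDCA only by formula and mass, and describes no separation step for TD-ESI anywhere. The protocol does have a chromatographic assay for stool bile acids, but it does not assign this check to it. UDCA may already be among that assay's analytes; the protocol does not list them.

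**Conclusion.** The point holds in two limited parts.

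1. The simvastatin figure is wrong as labelled. For the protocol's own formula the exact mass is 418.27 Da, and 418.57 Da is the average mass, 0.30 Da higher. This rests only on standard atomic masses. Whether it has any effect on detection is unknown.
2. The check as written does not say how UDCA is distinguished from CDCA and DCA, which have the same mass to any number of decimals. A signal at 392.29 Da is therefore not, on its own, evidence of drug carry-over. This rests on the isomers' formulas and on the absence of any described separation step. It would be answered if the missing pre-test figures show identification that truly separates the isomers.

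The severity is minor. The check supports attribution in the fecal-transplant mouse work, and no trial end point depends on it.

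**What to change.** - Change the simvastatin exact mass in Limitation 1 from 418.57 to 418.27 Da.
- Judge UDCA carry-over from the fecal LC-MS/MS assay already planned, with UDCA reported as its own chromatographically resolved analyte against a reference standard.
- Compare UDCA in the treated arms' six-month stool with their baseline stool and with control-arm stool, so that any UDCA signal present without treatment is accounted for.

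The cost is one corrected number and at most one added analyte in an existing assay. The small downside is a UDCA reference standard, if the assay does not already include one. The comparison samples are already collected under the study design.
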